- f) Height and body mass index (BMI) are collected at screening only.
- g) A (-) urine pregnancy test is required prior to oral lead-in at day 1 and prior to any injection and as required by Medical Monitor after a treatment interruption. A (+) urine test should be confirmed with a stat serum test. If (+), participant will need to be withdrawn. A Serum pregnancy test should be performed at any time pregnancy is suspected by the Investigator. Pregnant participants who remain in the study do not need pregnancy testing for the duration of the pregnancy see Appendix 15: Information and Guidance for Managing Pregnant Participants.
- h) Plasma for storage samples are collected for possible future analyses. Can be used for back-up in cases of loss/damage in transit, geno/pheno analyses for virologic failures. Only for women becoming pregnant and continuing on CAB LA+RPV LA as if pregnant a plasma HIV-1 RNA test and plasma for storage samples at Month 6 and Month 10 visits are required.
- i) All injections are 1 x CAB LA 600 mg IM + 1 x RPV LA 900 mg IM. Doses 1 and 2 are one month apart. Subsequent injections beginning at Dose 3 are every two months. The injections should be spaced approximately 2 cm from one another and from the site of any previous injection and/or any injection site

reaction. Bring RPV LA to approximately room temperature prior to injecting. Time and location of injection (right or left) as well as needle length used will be collected in the eCRF. IM dosing is expected to occur on the same date of the month as determined by IM Dose 1 visit date, this is the Target Date; where possible, this first injection should be performed within 2 hours of taking the last oral regimen dose. For Dose 2, a dosing window of +0 / -7 days from the target visit date is stipulated. A (+ or -) 7-day window from the target date visit is stipulated for IM dosing beginning at Dose 3. All decisions regarding dose interruption/ resumption must be discussed with the Medical Monitor in advance.

- Length of study visit from arrival until departure from clinic will be evaluated. Participant's time of arrival, actual start time of the appointment, and actual end time of the appointment will be collected in the eCRF.
- k) Questionnaires should be completed before receiving the injections.

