HIV-1 infected participants who meet all eligibility criteria will be switched from their pre-baseline regimen to an oral regimen (CAB 30 mg + RPV 25 mg once daily) during the **oral lead-in phase**. Participants will return to the clinic, and if laboratory and clinical evaluations continue to support progression into the **injection treatment phase** of the study, will take the last dose of their oral regimen (CAB 30 mg + RPV 25 mg) and receive the first dose of CAB LA (600 mg) + RPV LA (900 mg) injections on the same day (Month 1). The participant will receive the second injections CAB LA (600 mg) + RPV LA (900 mg) one month later (Month 2). All subsequent injections will occur every two months thereafter (Month 4, Month 6, etc) for a total of 7 doses of CAB LA

and RPV LA (Table 7). The total length of the treatment phase is approximately one year.

Table 7 Dosing Regimen

Oral Lead-in to End of Study ⁺		
CAB + RPV Oral Lead-In		
Oral Lead-in (Day 1 to Month 1)	• Take one tablet of CAB 30 mg + RPV 25 mg once daily	
two once daily tablets taken with food		
CAB LA + RPV LA Injections		
Dose 1 (Month 1)	Receive last dose of oral CAB + RPV regimen	
	 Receive CAB LA 600 mg given as 1 X 3 mL IM injection 	
	 Receive RPV LA 900 mg given as 1 X 3 mL IM injection 	
Dose 2 to Dose 7 (Month 2- End of Study ⁺)	 Receive CAB LA 600 mg given as 1 X 3 mL IM injection 	
two 3 mL injections every two months	 Receive RPV LA 900 mg given as 1 X 3 mL IM injection 	
+Until after dose 7 (Month 12) when locally approved and commercially available, the participant no longer derives clinical benefit, the participant meets a protocol-defined reason for discontinuation or until development of CAB LA or RPV LA is terminated		

The dosing window for the second injections will be +0/-7 days from the projected target date (target date is established at Month 1). All subsequent injection windows (starting with Dose 3) will be +7/-7 days from the projected target date. Doses outside of the window *may* be allowed with prior Medical Monitor approval.

Participants will continue CAB LA + RPV LA until:

- After dose 7 and when the study intervention is locally approved and available for the Investigator to prescribe. Note if intervention is not locally approved at dose 7 they will continue into the Extension Phase (see Section 6.8).
- the participant no longer derives clinical benefit
- the participant meets a protocol-defined reason for discontinuation

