6.5.3. IM Dosing

Participants receiving CAB LA and/or RPV LA are anticipated to be at risk for development of virologic resistance if antiretroviral therapy is interrupted. The time period during which participants are at risk for development of virologic resistance may be determined by the period between when drug levels fall below therapeutic values and when they fall below levels which exert selective pressure on HIV. This time period will vary by ART agent and is dependent upon effective concentration, inhibitory concentration, and half-life. Plasma concentrations of both LA drugs may be measurable for more than one year following IM injections. Any interruption in IM dosing should be discussed with the Medical Monitor. Investigators should ensure that the participant initiates alternative highly active ART to minimize the risk of developing resistance as concentrations of and RPV decline over time.

CAB LA + RPV LA dosing for participants transitioning from oral CAB + RPV is as follows:

All injections should be planned as single injections per drug.

Target Date

The patient's 'target date' is determined by their first injection date and ideally is the same date for every injection. For example, if the1st dose (Month 1) is January 15th, then dose 2 (Month 2) will be February 15th, and dose 3 (Month 4) will be April 15th, etc.

Since the first injection visit (Month 1) will determine the future injection visit schedule for participants and ideally be between the 1st and 28th day of the month. Planning for the first injection visit date (within allowed visit windows) should take into consideration the availability of the participants to adhere to future visit windows (planned vacations, business trips, *etc.*).

Treatment Injections- Months 1 and 2 -one month apart

Participants will take the last dose of their oral (CAB 30 mg + RPV 25mg) and receive the first CAB LA (600mg) + RPV LA (900mg) injections (within 2 hours of the final oral dose of CAB + RPV).

The second dose (CAB LA 600mg + RPV LA 900mg) will be administered one month later (preferable on the same target date as Dose 1). The dosing window for Dose 2 allows administration -7days of the proposed visit date but not later.

Treatment Injections- Months 4- Q2M dosing

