13.2. Appendix 2: Assessment Windows

13.2.1. Definitions of Assessment Windows for Analyses

Laboratory data, vital signs, adverse events, and genotypic/phenotypic data will be assigned to assessment windows according to actual dates rather than the nominal visit labels as recorded on the eCRF or in the laboratory database.

Prior to visit slotting, assessments are first assigned to a study phase (Screening, Intervention Phase, Extension, or Long Term Follow Up) as defined in [Appendix 3](#).

According to the protocol, the nominal target study visit date will be based on the first injection, the Month 1 date. For instance, if Month 1 occurred on July 7th, all subsequent visits are expected to occur on the 7th of each month such that subsequent visits will be August 7th, September 7th, October 7th, etc. Since there are not >28 days in every month of the year, if the Month 1 injection occurred on the 29th, 30th, or 31st of the month, then the target study visit date for the remainder of the visits will be the 28th of the month.

The nominal target study visit day is derived as

- **M1 Target Day** = Date of Actual M1 Injection Visit Date – Date of First Oral lead-in Dose + 1, if subject receives M1 injection; else M1 Target Day = 30.
- **Mx Target Day** = Mx Nominal Target Study Visit Date – Date of First Oral lead-in Dose + 1, for x=2,3, ...

Assessment windows will be derived based on the midpoint between two consecutive planned target study visit dates. For the Snapshot efficacy data, the same approach will be used, except for Month 12, which will use a +/- 6-week window around the projected target study visit date at Month 12.

For parameters which are not scheduled to be assessed at visits, the all-inclusive assessment windows will still be used; however, data summaries will only report scheduled visits. Assessments at unscheduled visits will be included in summaries of worst-case values across visit (e.g. during the intervention phase) and in data listings, as well any algorithms that make use of additional data (e.g., Snapshot).

For participants transitioning to commercial product at EOS, the safety follow-up visit date will be the last date referenced and serve as the ending timepoint for the final visit window.

Table 1 Assessment Windows for Screening, Intervention and Extension Phase Data (Excluding HIV-1 RNA)

Target (Study Day)	Analysis Window		Analysis Timepoint
	Beginning Timepoint	Ending Timepoint	

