13.5.2. Study Population

Demographics
Age

 Age, in whole years, will be calculated with respect to the subject’s Screening visit. GSK standard IDSL algorithms will be used for calculating age where birth date will be imputed as follows: 
 Any subject with a missing date and month will have this imputed as ‘30th June’. Birth date will be presented in listings as ‘YYYY’. Completely missing dates of birth will remain as missing, with no imputation applied. Consequently, the age of the subject will not be calculated and will remain missing.
Body Mass Index

 Calculated as Weight (kg)/Height (m)²
Hepatitis Status

 Hepatitis C status will be determined using antibody and/or hepatitis C virus (HCV) RNA assessments performed during screening or during the conduct of the study. If both antibody and virus RNA assessments are available, then the latter will take precedence and positive/negative status will be based on whether HCV RNA is detectable (i.e., ≥ limit of quantification) or not. A participant will be considered positive for hepatitis B virus (HBV) if they have a positive surface antigen or detectable HBV DNA result. “HBV DNA DETECTED” in the lab comment takes precedence over HBV DNA test result for positive hepatitis B status; for example, if a participant has HBV DNA test result below level of detection and the lab comment shows that HBV DNA detected, this participant will be considered positive for hepatitis B. If HBV DNA result is available, it will be used to qualify hepatitis B status as positive or negative (positive if ≥ limit of quantification); otherwise Hepatitis B status will be determined using the surface antigen result. Hepatitis status at entry will be based on the assessments prior to/on the start of the study treatment.
Adherence to CAB/RPV Injection Schedule

 Timeliness of Injections relative to Date of Projected Dosing Visits are assessed by using "actual injection visit date - projected visit date from first injection". The injections of interest in adherence

Demographics

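### For first injections on days 29 to 31 the SAP moves later target dates to the 28th, the protocol does not, and the adherence derivation does not say which date it uses

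*SAP*

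**What the plan says.** **Protocol.** Footnote i of the Schedule of Activities defines the target date: "IM dosing is expected to occur on the same date of the month as determined by IM Dose 1 visit date". Section 6.5.3 says the target "is determined by their first injection date and ideally is the same date for every injection". The same section advises that the first injection "ideally be between the 1st and 28th day of the month", but it does not forbid days 29 to 31 and gives no rule for a month that lacks the date. Section 4.3.3 sets the windows: "The dosing window for the second injections will be +0/-7 days from the projected target date", and "All subsequent injection windows (starting with Dose 3) will be +7/-7 days from the projected target date".

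**SAP.** Section 13.2.1 attributes its target date to the protocol, then adds for first injections on days 29 to 31: "then the target study visit date for the remainder of the visits will be the 28th of the month". SAP 13.1.1 reprints protocol footnote i with the same-date definition and no such exception. SAP 13.5.2 derives timeliness of injections as "actual injection visit date - projected visit date from first injection". It refers to protocol Section 4.3.3 for out-of-window status and does not say how the projected date is obtained. The 28th rule is not among the changes listed in SAP 2.1.1.

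**The concern.** The percentage of injections within the target window is a named secondary endpoint, the measure of fidelity to the dosing schedule. Sites schedule against one target date. If the analysis scores against another, some injections that meet the protocol are labelled late and some that miss it are labelled on time. Dose 2 is the sensitive case because it has no tolerance after the target, so a shift of one day is enough to change its status.

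Adherence is tabulated by visit, country and site (SAF_T1) and by subgroup, including implementation strategy (SAF_T2). With 474 enrolled over 18 sites, an average site has 474/18 = 26 patients. One reclassified Dose 2 then moves that site's Month 2 figure by 1/26, about 4 percentage points.

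**Working it through.** **Inputs.** Target-date rules from protocol footnote i, protocol 6.5.3 and SAP 13.2.1; windows of +0/-7 (Dose 2) and +7/-7 (Dose 3 onward) from protocol 4.3.3; 474 patients enrolled from SAP 2.4.1. Doses 2 to 7 fall 1, 3, 5, 7, 9 and 11 months after Dose 1.

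**Step 1: the documents' own examples.** Protocol 6.5.3: a first injection on 15 January gives 15 February and 15 April. SAP 13.2.1: 7 July gives 7 August, 7 September and 7 October. Taking the same day of the month reproduces both. For days 1 to 28 the two documents agree at every dose, so the question concerns days 29 to 31 only.

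**Step 2: the shift.**

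Shift = protocol target - SAP target = min(day of Dose 1, last day of the target month) - 28.

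The cap at the last day of the month is an assumption of this check, needed because the protocol has no rule for a missing date.

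| Dose 1 | Dose 2, protocol | Dose 2, SAP 28th rule | Score if given on protocol target |
|---|---|---|---|
| 29 March 2021 | 29 April | 28 April | +1 |
| 30 March 2021 | 30 April | 28 April | +2 |
| 31 July 2021 | 31 August | 28 August | +3 |
| 30 January 2021 | no such date (28 February assumed) | 28 February | 0 |

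**Step 3: one patient, Dose 1 on 30 March 2021.**
- Dose 2: protocol window 23 to 30 April; window around the SAP date 21 to 28 April. Injections on 29 and 30 April become late. Injections on 21 and 22 April, 9 and 8 days early by the protocol date, become in window.
- Dose 3: protocol target 30 June, window 23 June to 7 July; SAP target 28 June, window 21 June to 5 July. Injections on 6 and 7 July score +8 and +9. Injections on 21 and 22 June, 9 and 8 days early by the protocol date, score -7 and -6.

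With a shift of 3 days, the falsely in-window range reaches 10 days early.

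**Step 4: share of compliant days that change status.** In 2021 there are 29 first-injection dates on days 29 to 31.
- Dose 2: the shift is 0 on 3 dates, 1 on 10, 2 on 14 and 3 on 2. Days scored late: 10x1 + 14x2 + 2x3 = 44. Compliant days: 29x8 = 232. Share 44/232 = 19%.
- Doses 3 to 7: 29x5 = 145 targets, with shift 0 on 13, 1 on 50, 2 on 60 and 3 on 22. Days scored beyond +7: 50x1 + 60x2 + 22x3 = 236. Compliant days: 145x15 = 2175. Share 236/2175 = 11%.

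The same count for a leap year (2020) gives 48/240 = 20% and 241/2250 = 11%.

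**Step 5: patients.** If first injections were spread evenly over the calendar: 474 x 29/365 = 37.7 (7.9%), or 474 x 30/366 = 38.9 (8.2%) in a leap year. The day 1 to 28 preference lowers this, possibly to zero, so the range is 0 to about 39.

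If, in addition, every Dose 2 were compliant and spread evenly over its eight allowed days, 37.7 x 0.19 = about 7 would change status. Both even spreads are assumptions.

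**The case against.** The strongest reply is that the 28th rule may never reach the adherence tables. SAP 13.2.1 opens by limiting its scope to laboratory data, vital signs, adverse events and resistance data, and it feeds the visit-slotting windows. Adherence is derived separately in 13.5.2 without citing 13.2.1, and SAP 13.1.1 carries the protocol's same-date definition for injections. A programmer who used that definition would misscore nothing. This stands as far as it goes: a reader might infer that the SAP definitely scores compliant injections late, and the documents do not say so. However, 13.2.1 is the SAP's only operational derivation of visit dates from the first injection, and it itself speaks of a projected target date. The same-date definition also cannot be programmed as written for, say, a first injection on 31 March, because there is no 31 April. Applying the 28th rule is therefore the natural reading, and 13.5.2 needs a definition either way.

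Three further inferences are tempting and not supported:

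- **That the Dose 2 error runs one way only.** It does not: some injections 8 to 10 days early become in window.
- **That an ordinary late-scored Dose 2 would appear in the out-of-window displays.** At +1 to +3 it falls in the row for 1 to 7 days. The late out-of-window row in SAF_T1 and SAF_T2 counts from +7 in every column, Month 2 included. The separate categories in 13.5.2 cover only bridging or COVID-related cases. It fails only under the +0 limit of protocol 4.3.3.
- **That the comparison between implementation arms is biased.** Nothing in the documents ties day of first injection to arm.

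**Conclusion.** The two documents state different target dates for first injections on days 29 to 31, by up to 3 days, and the SAP contains both. The adherence derivation rests on a projected date that it leaves undefined. Conditional on the 13.2.1 date being used:

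- a Dose 2 given on its protocol target fails the +0 limit, except in a 28-day February;
- compliant Doses 3 to 7 in the last 1 to 3 days of their window score beyond +7;
- some early injections score as in window.

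The size is limited. At most about 8% of patients (0 to about 39 of 474) could be affected, assuming evenly spread first injections, and for them about 19% of compliant Dose 2 days and 11% of compliant Dose 3 to 7 days change status. The counts assume the last day of the month where the protocol date does not exist. The point merits correction because it concerns a prespecified secondary endpoint reported by site, where small numbers show.

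**What to change.** Reconcile protocol footnote i and Section 6.5.3 with SAP 13.2.1, so that one target date applies to first injections on days 29 to 31, including months that lack that date. Which date that is, whether the 28th, the last day of the month or another rule, is for the sponsor to decide. The protocol currently contains neither of the first two.

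Then define the projected visit date in SAP 13.5.2 as that same date, the one given to sites. Use it for the fidelity endpoint, SAF_T1 and SAF_T2, in place of a separate 28th rule that exists only in the analysis.

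The cost is a short clarification in each document and a date function in the derivation code. No new data are needed.

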Day of earliest record	Assessment Study Day ≤ 1		Screening
For subjects discontinuing prior to receiving first injection:			
30	Assessment Study Day = 2	Study Day of Last CAB/RPV Oral Dose+1	Month 1
	Assessment Study Day > (Study Day of Last CAB/RPV Oral Lead-in Dose +1)		Follow-up
For subjects receiving first injection:			
Day of First Injection	Study Day = 2	M1 target day + $\text{floor} [(M2 \text{ target day} - M1 \text{ target day})/2]$	Month 1
M2 Target Day	M1 target day + $\text{floor} [(M2 \text{ target day} - M1 \text{ target day})/2] + 1$	M2 target day + $\text{floor} [(M4 \text{ target day} - M2 \text{ target day})/2]$	Month 2
M4 Target Day	M2 target day + $\text{floor} [(M4 \text{ target day} - M2 \text{ target day})/2] + 1$	M4 target day + $\text{floor} [(M6 \text{ target day} - M4 \text{ target day})/2]$	Month 4
M6 Target Day	M4 target day + $\text{floor} [(M6 \text{ target day} - M4 \text{ target day})/2] + 1$	M6 target day + $\text{floor} [(M8 \text{ target day} - M6 \text{ target day})/2]$	Month 6
M8 Target Day	M6 target day + $\text{floor} [(M8 \text{ target day} - M6 \text{ target day})/2] + 1$	M8 target day + $\text{floor} [(M12 \text{ target day} - M8 \text{ target day})/2]$	Month 8
M10 Target Day	M8 target day + $\text{floor} [(M10 \text{ target day} - M8 \text{ target day})/2] + 1$	M10 target day + $\text{floor} [(M12 \text{ target day} - M10 \text{ target day})/2]$	Month 10
M12 Target Day	M10 target day + $\text{floor} [(M12 \text{ target day} - M10 \text{ target day})/2] + 1$	M12 target day + $\text{floor} [(M14 \text{ target day} - M12 \text{ target day})/2]$	Month 12
Mx Target Day	M(x-2) target day - $\text{floor} [(Mx \text{ target day} - M(x-2) \text{ target day})/2] + 1$	Mx target day + $\text{floor} [(M(x+2) \text{ target day} - Mx \text{ target day})/2]$	Month x For x = 14, 16, etc.
For subjects who permanently discontinue study treatment:			
	Assessment Study Day > Min (LTFU ART Start Date, Max (Study Day of Last Dose of Oral Study Treatment (CAB+RPV or SOC Bridging) + 1, Study Day of Last CAB + RPV Injection + 63))		Follow-up

Table 2 Assessment Windows for Screening and Intervention Phase HIV-1 RNA Data

Target (Study Day)	Analysis Window		Analysis Timepoint
	Beginning Timepoint	Ending Timepoint	
Day of earliest record	Assessment Study Day \leq 1		Screening
For subjects discontinuing prior to receiving first injection:			
28	Assessment Study Day = 2	Study Day of Last Oral Lead-in Dose +1	Month 1

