	Assessment Study Day > (Study Day of Last CAB/RPV Oral Lead-in Dose + 1)		Follow-up
For subjects receiving first injection:			
Date of First Injection	Study Day = 2	M1 target day + $\text{floor} [(M2 \text{ target day} - M1 \text{ target day})/2]$	Month 1
M2 Target Day	M1 target day + $\text{floor} [(M2 \text{ target day} - M1 \text{ target day})/2] + 1$	M2 target day + $\text{floor} [(M4 \text{ target day} - M2 \text{ target day})/2]$	Month 2
M4 Target Day	M2 target day + $\text{floor} [(M4 \text{ target day} - M2 \text{ target day})/2] + 1$	M4 target day + $\text{floor} [(M6 \text{ target day} - M4 \text{ target day})/2]$	Month 4
M6 Target Day	M4 target day + $\text{floor} [(M6 \text{ target day} - M4 \text{ target day})/2] + 1$	M6 target day + $\text{floor} [(M8 \text{ target day} - M6 \text{ target day})/2]$	Month 6
M8 Target Day	M6 target day + $\text{floor} [(M8 \text{ target day} - M6 \text{ target day})/2] + 1$	M8 target day + $\text{floor} [(M10 \text{ target day} - M8 \text{ target day})/2]$	Month 8
M10 Target Day	M8 target day + $\text{floor} [(M10 \text{ target day} - M8 \text{ target day})/2] + 1$	M12 target day - 43	Month 10
M12 Target Day	M12 target day - 42	M12 target day + 42	Month 12
M14 Target Day	Assessment Study Day > M12 target day + 42		Month 14
For subjects who permanently discontinue study treatment during the Intervention Phase:			
	Assessment Study Day > Min (LTFU ART Start Date, Max (Study Day of Last Dose of Oral Study Treatment (CAB+RPV or SOC Bridging) +1, Study Day of Last CAB + RPV Injection + 63))		Follow-up

Table 3 Assessment Windows for Extension Phase HIV-1 RNA Data

Target (Study Day)	Analysis Window		Analysis Timepoint
	Beginning Timepoint	Ending Timepoint	
M14 Target Day	Study Day of Nominal Week 14 Visit	M14 target day - floor [(M16 target day – M14 target day)/2]	Month 14
M16 Target Day	M14 target day - floor [(M16 target day – M14 target day)/2] + 1	M16 target day + floor [(M18 target day – M16 target day)/2]	Month 16
Mx Target Day	M(x-2) target day - floor [(Mx target day – M(x-2) target day)/2] + 1	Mx target day + floor [(M(x+2) target day – Mx target day)/2]	Month x For x =18, 20 etc.
For subjects who permanently discontinue study treatment during the Extension Phase:			
	Assessment Study Day > Min (LTFU ART Start Date, Max (Study Day of Last Dose of Oral Study Treatment (CAB+RPV or SOC Bridging) +1, Study Day of Last CAB + RPV Injection + 63))		Follow-up

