13.5. Appendix 5: Derived and Transformed Data

13.5.1. General

Multiple Measurements at One Analysis Time Point
 
 • If there are two values within a time window (as per Section 13.2.1) the value closest to the target day for that window will be used. If values are the same distance from the target, then the mean (geometric mean for HIV-1 RNA, arithmetic mean for all other measurement) will be taken. • Assessments not chosen for use in summary statistics by this algorithm will still appear in the associated listings. • All applicable valid assessments, irrespective of proximity to the target study day, will be used when categorizing values across visits, such as ‘maximum grade during the intervention phase’ or ‘at any time post-baseline’, and for any algorithm that has specific rules for which observation to use (e.g. snapshot algorithm, LOCF or CVF identification). • Participants having both High and Low values for Normal Ranges at any post-baseline visit for safety parameters will be counted in both the High and Low categories of “Any visit post-baseline” row of related summary tables. This will also be applicable to relevant Potential Clinical Importance summary tables.

Treatment Start Date
 
 • Intervention Phase Treatment Start Date = Earliest date of CAB + RPV oral lead-in entered in the IP exposure eCRF form

Nominal Month 14 Visit Date
 
 • For participants who received Month 14 injection, the nominal Month 14 visit date is defined by the Month 14 injection date. • Otherwise, nominal Month 14 visit date is defined by the date of latest Month 14 assessment. • For participants who continued into Extension Phase but missed the Month 14 visit, the nominal Month 14 visit date is defined by the last contact date prior to the date of the first nominal extension phase visit (i.e. Month 16, Month 18, etc.).

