13.12. Appendix 12: List of Data Displays

All data displays will use the term “subject” rather than “participant” in accordance with CDSIC and GSK Statistical Display Standards.

Where applicable, all summary displays will present data across both the Intervention and Extension phases unless explicitly stated otherwise in the display title.

At EOS, the RAPIDO Data Viewer will be produced to allow for the clinical team to review ADaM data directly related to adverse events, exposure, HIV-1 RNA, and labs. This will take the place of some, previously standard generic listings from these categories. Listings including results of pregnancy details will only be included if a pregnancy occurs.

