3.15.	Safety	AE3	Summary of Common ($\geq 5\%$) Adverse Events by Overall Frequency	ICH E3	M12, EOS
3.16.	Safety	AE3	Summary of Common ($\geq 1\%$) Grade 2-5 Adverse Events by Overall Frequency	ICH E3	M12, EOS

CONFIDENTIAL

213199

Safety: Tables					
3.17.	Safety	201584/primary_7/T3.46	Summary of Adverse Events by Visit and Maximum Severity – Overall and Common		HL, M12, EOS
3.18.	Safety	AE3	Summary Drug-Related Adverse Events by Overall Frequency	ICH E3	M12, EOS
3.19.	Safety	AE5B	Summary of Drug-Related Adverse Events by System Organ Class and Maximum Grade	ICH E3	HL, M12, EOS
3.20.	Safety	AE5B	Summary of Drug-Related Adverse Events by System Organ Class and Maximum Grade (Oral Lead-in Period)	ICH E3	M12
3.21.	LTFU	AE5B	Summary of Drug-Related Adverse Events by System Organ Class and Maximum Grade (Long Term Follow-up Period)	ICH E3	M12, EOS
3.22.	Safety	AE5B	Summary of Drug-Related Adverse Events by System Organ Class and Maximum Grade — Excluding Study Drug Injection Site Reactions		M12, EOS
3.23.	Safety	AE15	Summary of Common ($\geq 5\%$) Non-serious Adverse Events by System Organ Class and Preferred Term (Number of Subjects and Occurrences)	FDAAA, EudraCT	M12, EOS
3.24.	Safety	AE3	Summary of Common ($\geq 1\%$) Drug-Related Grade 2-5 Adverse Events by Overall Frequency	ICH E3	M12, EOS
3.25.	Safety	AE3	Summary of Non-Serious Drug-Related Adverse Events by Overall Frequency	Plain Language Summary requirements.	M12, EOS
3.26.	Safety	201584/primary_7/T3.46	Summary of Drug-Related Adverse Events by Visit and Maximum Severity – Overall and Common		M12, EOS
Serious and Other Significant Adverse Events					
3.27.	Safety	AE5B	Summary of Serious Adverse Events by System Organ Class and Maximum Grade	ICH E3	HL, M12, EOS

CONFIDENTIAL

213199

Safety: Tables					
3.28.	Safety	AE5B	Summary of Serious Adverse Events by System Organ Class and Maximum Grade (Oral Lead-in Period)	ICH E3	M12
3.29.	LTFU	AE5B	Summary of Serious Adverse Events by System Organ Class and Maximum Grade (Long Term Follow-up Period)	ICH E3	M12, EOS
3.30.	Safety	AE16	Summary of Serious Adverse Events by System Organ Class and Preferred Term (Number of Subjects and Occurrences)	FDAAA, EudraCT	M12, EOS
3.31.	Safety	201584/primary_7/T3.46	Summary of Serious Adverse Events by Visit and Maximum Severity – Overall and Common		M12, EOS

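### Several SAP assessment-window formulas break the SAP's own midpoint rule, so windows overlap or are empty, and Snapshot step 3.2.1 still uses 35 days where the rest of the SAP uses 63

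*SAP*

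**What the plan says.** SAP Section 13.2.1 gives one general rule: "Assessment windows will be derived based on the midpoint between two consecutive planned target study visit dates". The only stated exception is Month 12 for Snapshot, which uses ±6 weeks. Records, including adverse events, are slotted by actual date after being assigned to a study phase.

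The tables that follow do not all apply this rule:

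- **Table 1, Month 8 end:** "M8 target day + $\text{floor} [(M12 \text{ target day} - M8 \text{ target day})/2". The next row starts Month 10 at the Month 8–10 midpoint plus one day. Table 2 uses the Month 10 target for the same Month 8 bound.
- **Table 1, start of Month x (x = 14 and later):** "M(x-2) target day - $\text{floor} [(Mx \text{ target day} - M(x-2) \text{ target day})/2] + 1". Table 3 has the same minus sign from Month 16 on.
- **Table 3, Month 14:** starts at "Study Day of Nominal Week 14 Visit" and ends at "M14 target day - floor [(M16 target day – M14 target day)/2".

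On the end of treatment, the follow-up rows of Tables 1–3, the on-treatment definition in Table 11 and the exposure formulas all use last injection +63 days. The reasons given for SAP Amendment 1 state that 63 replaced 35. Snapshot step 3.2.1 (Section 13.8) and the Figure 2.3 programming note (Section 13.12.6), which Figure 2.4 reuses, still have 35.

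**The concern.** A programmer has to choose between the rule in the text and the formula in the cell, and the two give different visit assignments. The tie-break in Section 13.5.1, under which "the value closest to the target day for that window will be used", chooses between values inside one window. No rule was found for one record that lies in two windows.

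The most exposed outputs are the by-visit adverse event tables. Table 3.17, "Summary of Adverse Events by Visit and Maximum Severity – Overall and Common", is due at headline, Month 12 and end of study. Tables 3.26, 3.31 and 3.35 are due at Month 12 and end of study. Their titles name no phase, so Section 13.12 applies: "all summary displays will present data across both the Intervention and Extension phases unless explicitly stated otherwise in the display title". Tables 2.3 and 2.4 are expanded to all visits at end of study, which brings in the Table 3 windows.

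The 35 days matter in a different way. In Snapshot the on-treatment status of a viral load follows Section 13.3 (+63), but the test of whether a participant without a viral load is still on study uses +35. The two can disagree for the same person.

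**Working it through.** **Inputs.** Write T8 for the study day of the Month 8 target, and so on. By Section 13.2.1, targets fall on the same day of the month as Dose 1, days 29–31 move to the 28th, and study day counts from the first oral dose. Injections from Dose 3 are permitted within ±7 days of target (Protocol Section 4.3.3).

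**Worked example** (assumed dates: oral start 15 January 2021, Dose 1 15 February 2021). Targets: M1 = 32, M6 = 182, M8 = 244, M10 = 305, M12 = 366, M14 = 425, M16 = 486, M18 = 547, M20 = 609.

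| Window | As printed | By the midpoint rule |
|---|---|---|
| Table 1 Month 8 | 182+31+1 = 214 to 244+floor(122/2) = 305 | 214 to 244+floor(61/2) = 274 |
| Table 1 Month 10 | 244+30+1 = 275 to 305+30 = 335 | same |
| Tables 1 and 3 Month 16 | 425−30+1 = 396 to 486+30 = 516 | 425+30+1 = 456 to 516 |
| Tables 1 and 3 Month 18 | 486−30+1 = 457 to 547+31 = 578 | 486+30+1 = 517 to 578 |
| Table 3 Month 14 (visit on target) | 425 to 425−30 = 395 | 425 to 425+30 = 455 |

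Months 8 and 10 share days 275–305 (31 days). Months 16 and 18 share days 457–516 (60 days), and the Month 16 target, day 486, lies in both. The Table 3 Month 14 window ends before it starts, so a Month 14 viral load on day 425 falls in Month 16.

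**All dates.** The same formulas were evaluated for each of the 1,461 Dose 1 dates from 1 January 2021 to 31 December 2024, with oral start 31 days earlier.

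- Months 8 and 10 overlap by 31 days for 1,032 dates, 30 for 336 and 29 for 93. That is 7.3–7.9% of the days from day 2 to the end of Month 12. Of the 15 permitted Dose 6 days, 6–9 lie in both windows.
- Consecutive windows overlap by 58–62 days from Months 14/16 on. Between the M14 and M24 targets, 98.7% of days lie in two windows. The Month 12/14 overlap disappears if Month 14 is applied to Extension records only. The others do not, because Months 8 and 10 are both Intervention and Months 14, 16 and 18 are all Extension.
- Table 3 Month 14 ends 29–31 days before its target, which is 22–24 days before the earliest permitted injection (M14−7).
- With the signs and the Month 8 bound corrected, no windows overlap.

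**Snapshot step 3.2.1.** After permanent discontinuation with no on-treatment viral load in the Month 12 window, a participant counts as on study only if the upper bound M12+42 precedes the treatment-end date. Let L be the last injection day, with no later oral treatment and LTFU ART starting after M12+42.

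- With +35: M12+42 < L+35 requires L ≥ M12+8. None of the 15 permitted Dose 7 days qualifies.
- With +63: M12+42 < L+63 requires L ≥ M12−20. All 15 qualify.
- The results differ for L from M12−20 to M12+7, which is 28 days.

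In the example the window ends on day 366+42 = 408. For L = 366 the bounds are 401 (fails) and 429 (passes). A participant who fails goes to step 3.2.2. There, a non-safety withdrawal with last on-treatment viral load ≥50 c/mL is counted as ≥50 instead of no virologic data. Each such move is 1/450 = 0.22 percentage points.

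**Figure 2.3/2.4 line.** The note takes a minimum that includes last oral CAB+RPV +1. Without oral bridging, the last oral dose is on the Dose 1 day (32), so the line falls at day 33. The rule used in the windows gives max(366+63, 33) = 429, unless LTFU ART starts earlier.

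**The case against.** The strongest reply is that many of these windows are not reported. Sections 13.2.1 and 13.4.2 limit summaries to scheduled visits. Laboratory tests, vital signs and HIV-1 RNA are not scheduled at Month 10, and footnote b of the schedule carries that pattern to Months 14, 18 and 22. Taken alone, the printed Table 1 windows for Months 12, 16, 20 and 24 do not overlap. An HIV-1 RNA at Month 14 arises only for a pregnant participant or an unscheduled test, and where a Month 16 value exists the closest-to-target rule would usually prefer it. The shell for the by-visit adverse event tables is not in the documents, so its exact slotting cannot be confirmed, and adverse events are not actively sought at Month 10. For Snapshot, the Protocol's two months ±7 days is a limit within which HAART starts. An earlier start can make 35 versus 63 irrelevant. The figure line changes no estimate.

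These points limit the size of the problem but do not remove it. A record on the scheduled Month 16 target day also lies in the Month 18 window for every date tested, and nothing in the SAP says it belongs to Month 16. If placed in Month 18 it would not be reported at all. Section 13.2.1 slots adverse events by date, and Table 1 has its own Month 10 row, so the Month 8 bound cannot be read as a deliberate skip. A Month 12 dosing visit without a viral load is possible: Protocol Section 10.14.1 permits injections with few or no other assessments under COVID-19 constraints.

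**Conclusion.** The concern holds. Followed literally, Tables 1 and 3 give two visits for many records and an empty Month 14 window for extension HIV-1 RNA, and Snapshot uses two different treatment-end rules.

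The consequences are confined to secondary outputs: by-visit adverse event tables, unscheduled tests, extension-phase data, and the reason categories in Snapshot. The Month 12 <50 c/mL count cannot change, because step 3.2.1 applies only when there is no on-treatment viral load in the window. Intervention-phase HIV-1 RNA windows (Table 2) have no overlap. The primary staff analysis does not use these tables. Scheduled laboratory and vital-sign summaries are essentially unaffected provided each record is given to its scheduled visit.

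The overlap lengths follow from the calendar and the printed formulas. Two readings are assumed: that Week 14 in Table 3 means Month 14, since the study has no Week 14 visit, and, for the Snapshot contrast, that LTFU ART starts after M12+42. The documents do not say how many participants would be reclassified. On the planned 474 enrolled instead of 450, each would count 0.21 points.

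**What to change.** Make these corrections before the affected outputs are programmed or rerun:

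- **Table 1, Month 8 end:** T8 + floor[(T10 − T8)/2].
- **Tables 1 and 3, start of Month x** (including the Month 16 row of Table 3): T(x−2) + floor[(Tx − T(x−2))/2] + 1.
- **Table 3, Month 14:** from the nominal Month 14 visit to T14 + floor[(T16 − T14)/2].
- **Snapshot step 3.2.1:** replace 35 by 63.
- **Figure 2.3 note (and so 2.4):** min(LTFU ART start, max(last injection + 63, last oral study treatment + 1)).

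That is six table cells, one Snapshot line and one note, plus the matching programs. No data collection is involved.
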